### **Analytical Plan**

- For the feasibility portion of the study, we will describe descriptive results of subjects' time of use of the monitor, their description of ease of use (difficult or easy), and the quantity of non-artifactual VS data.
- Results will be analyzed initially using descriptive statistics (percent of time VS remained in one of the ranges listed in Table 2) and means/standard error.
- We will compare relative incidence with matched cohort undergoing surgery using univariate analyses (categorical variables: chi-square test, continuous variables: Student's t-test or Mann-Whitney U test). We will use multivariable Cox proportional hazards regression modeling to assess VS risk factors associated with the postoperative undesired outcomes mentioned in outcome measures above.
- Statistical methods data will be expressed as mean  $\pm$  SD, number (percentage), odds ratio, and 95% CI. All P values will be two-tailed, and a P value less than 0.05 is considered significant.

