**Objectives**

Using a portable, wireless multi-Vital Sign (VS) monitoring system developed by Caretaker Medical, we have several objectives:

- Primary:
  - Assess the feasibility of placing a Caretaker monitor on subjects scheduled for surgery for an 18-24 hour preoperative ambulatory monitoring session.
  - Assess the feasibility of placing a Caretaker monitor on subjects scheduled for surgery for the perioperative period defined as 18-24 hour intraoperative and postoperative ambulatory monitoring session.
  - Quantitate the data capture rate (estimated at over 99% in the company's prior studies) in this setting and how reliable our monitor return rate is in this setting.
- Secondary:
  - Assess the prevalence of alterations in VS (HR, RR, SaO2, BP, Cardiac Output, Stroke Volume, and HRV preoperatively) in a group of our highest acuity patients (top quartile of risk score) undergoing non-cardiac surgical procedures requiring at least a 2-day admission.
  - Assess any correlation of concerning ambulatory preoperative VS to postoperative VS.
    - We estimate that the percent of time the patient experiences these concerning preoperative VS values will correlate with a higher risk for a similar range of VS postoperatively, as well as undesired outcomes.
      - Undesired outcomes are defined as a) 30-day mortality, b) longer length of stay, c) higher ICU transfer, and 4) RRT calls).

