## **Methods and Measures**

### **Design**

The Caretaker device is a wrist device that has a version that has already been approved by the FDA for use amongst medical professionals. For the conduct of this protocol we propose to use a newer version of the device called VitalStream, which has been cleared for use by the FDA.

The New Caretaker device being used in the study has successfully passed all safety and accuracy tests by an independent lab, which have been submitted to the FDA already (see attached Declaration of Conformity).

We plan to monitor ambulatory preoperative CareTaker VS (HR, RR, SaO2, BP, Cardiac Output, Stroke Volume, and HRV) in random patients who meet our inclusion criteria for 18-24 hours, beginning during their preoperative (Preoperative Assessment Clinic, PAC) visit then overnight after they leave. Postoperatively, we will measure these VS in the same patients for approximately 24 hours postoperatively.

These monitors transmit VS to a data cloud, where we will be able to store and then later analyze the VS data. Clinical data will be collected from our EPIC Information System in order to provide pre- and postoperative information to examine corresponding risk factors and provide demographics.

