### **Human Subjects Protection**

#### **Subject Recruitment Methods**

Subjects scheduled for surgery and to have a preoperative visit in our Preoperative Assessment Clinic (PAC) will be identified using their medical information in our EHR (Epic) to see if they fit our study criteria, and interviewed by research staff in the PAC. We ensure equal access to participation among women and minorities because we see both who fit our study criteria adequately on a daily basis. We will protect the privacy of potential subjects during recruitment by not using names or date of birth, and we will assign a unique study identifier to their medical record number.

- We do not plan to use recruitment flyers and advertisements.
- We will use limited PHI to identify subjects via medical records search.
  - We will use only the minimum amount of PHI necessary to review eligibility criteria and method to contact potential subjects. The information we plan to collect for this purpose includes:
    - Medical history
    - Planned surgical procedure

- Age
- PAC appointment time

Confidentiality/privacy will be protected prior to ascertaining desire to participate. Subjects who appear to be eligible for the study on the PAC appointment list will be marked for a conversation with a member of the study staff that will occur during their PAC visit. If they do not wish to participate, any record of their PHI will be immediately erased if electronic or shredded if on paper. **Informed Consent**

Signed informed consent will be obtained from each subject by a member of the study staff while the patients are present in the PAC.

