### **Data and Safety Monitoring**

Since this is a feasibility study of the Caretaker monitor, we will disable the data screen from displaying vital signs. Stored data will later be analyzed for proximity to standard vital signs measured during the subject's hospital stay. No vital signs from the monitor will be used for actionable interventions.

The principal investigator will be responsible for the overall monitoring of the data and safety of study participants. The principal investigator will be assisted by other members of the study staff.

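### The matched-cohort comparison is assigned tests that ignore the matching, and no stated objective calls for it; analyse it by matched set as a descriptive comparison, or remove it

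*Combined protocol and SAP*

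**What the plan says.** The matched cohort appears once, in the Analytical Plan: "We will compare relative incidence with matched cohort undergoing surgery using univariate analyses". The tests follow in parentheses: "categorical variables: chi-square test, continuous variables: Student's t-test or Mann-Whitney U test". The next sentence plans a multivariable Cox model relating vital-sign risk factors to the undesired postoperative outcomes. The section sets two-tailed P below 0.05 as significant.

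The documents do not give the cohort's source, matching variables, ratio or size. They do not say whether its members wear the monitor, or which event's incidence is compared.

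Three other places bear on the point:

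- **Objectives and Outcome Measures.** The primary aims are feasibility, data capture and monitor return. The secondary aims are the prevalence of altered vital signs in the high-risk group, the pre-to-postoperative relation ("Assess any correlation of concerning ambulatory preoperative VS to postoperative VS"), and the association of vital-sign ranges with undesired outcomes. None names a second cohort.
- **Design.** One group is followed through both phases: "Postoperatively, we will measure these VS in the same patients for approximately 24 hours postoperatively".
- **Data and Safety Monitoring.** "we will disable the data screen from displaying vital signs", and "No vital signs from the monitor will be used for actionable interventions".

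**The concern.** There are two problems.

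First, the tests do not fit the design. Matching is meant to make the two members of a pair alike. If it succeeds, their outcomes are positively correlated, and the difference between groups is estimated more precisely than an independent-samples formula assumes. Chi-square, Student's t and Mann-Whitney take no account of this, so the stated P values and confidence intervals do not correspond to the design.

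Second, the comparison has no stated purpose. The vital-sign objectives need vital-sign data on everyone compared. A cohort that never wore the device could contribute only outcomes held in the health record. Participants' monitor values are hidden and not acted on, so there is no planned route by which monitoring changes those outcomes. A difference would then reflect who consents, how well the matching worked, or chance. With a significance threshold attached and no stated question, the result could be misread as bearing on vital signs or on monitoring.

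**Working it through.** **Plan's own figure.** There is none for this comparison. The 150 patients under Sample Size are justified by a within-patient change from Phase 1 to Phase 2, so that figure does not bear on the matched cohort.

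**Inputs**

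| Input | Value | Source |
|---|---|---|
| Tests | independent-samples only | Analytical Plan |
| Significance level | 5%, two-sided | Analytical Plan |
| Matching | 1:1, individual | assumption |
| Within-pair correlation ρ | 0 to 0.5 | assumption |
| Pairs (simulation only) | 150 | assumption: one match per evaluable patient |
| Event rate (simulation only) | 10% and 20% | assumption |

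**Step 1: standard error.** With n pairs and outcome SD σ, the unpaired formula uses variance 2σ²/n for the difference. The true variance is 2σ²(1−ρ)/n. The unpaired standard error is therefore too large by a factor 1/√(1−ρ): 1/√0.8 = 1.12 at ρ = 0.2, and 1/√0.5 = 1.41 at ρ = 0.5. Confidence intervals for the difference are too wide by the same factor.

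**Step 2: true size.** Under the null the unpaired statistic has SD √(1−ρ), so size = 2 × [1 − Φ(1.96/√(1−ρ))]. At ρ = 0.2, 1.96/0.894 = 2.191, giving 2.8%. At ρ = 0.5, 1.96/0.707 = 2.772, giving 0.6%.

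**Step 3: power.** Take the effect for which a paired test has 90% power, that is 1.9600 + 1.2816 = 3.2416 true standard errors. The unpaired test then has power Φ(3.2416 − 1.96/√(1−ρ)). At ρ = 0.2 this is Φ(1.050) = 85%. At ρ = 0.5 it is Φ(0.470) = 68%.

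| ρ | True size of nominal 5% unpaired test | Unpaired power where paired has 90% |
|---|---|---|
| 0 | 5.0% | 90% |
| 0.1 | 3.9% | 88% |
| 0.2 | 2.8% | 85% |
| 0.3 | 1.9% | 82% |
| 0.5 | 0.6% | 68% |

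These two results do not depend on n.

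**Step 4: simulation with binary outcomes** (150 pairs, 100,000 runs, no true difference).

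| ρ | Chi-square size, event rate 10% / 20% | McNemar size, event rate 10% / 20% |
|---|---|---|
| 0 | 5.0% / 5.1% | 5.3% / 5.0% |
| 0.2 | 2.9% / 2.9% | 5.3% / 4.9% |
| 0.5 | 0.6% / 0.5% | 4.5% / 5.4% |

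The simulation agrees with the formula. McNemar's test stays near 5% throughout.

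**Step 5: what the comparison could inform.** This is a reading of the text, under the two possible meanings.

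- *Separate cohort.* Every participant has surgery, so a cohort described only as having surgery reads most naturally as another group. Under Interventions and Interactions, only those who agree to enter are fitted with the monitor. Such a cohort has no range, capture or return data, so only health-record outcomes can be compared.
- *Matching among participants*, for example those with and without concerning vital signs. This would bear on the outcome linking ranges to undesired outcomes. It cannot be run as written: Table 2 marks no range as concerning, no percent-of-time cut-off defines exposure, and no matching variables are named.

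**The case against.** The strongest reply is that the documents never say the cohort is unmonitored. Matching among participants is not excluded, and on that reading the comparison could serve the outcome on vital-sign ranges. The disabled display would not matter either, because the data are stored for later analysis. This stands. A reader might infer that the cohort certainly lacks monitor data and that the comparison can answer no objective at all. The documents support that only conditionally, if the cohort is unmonitored.

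A reader might also infer that ignoring the matching inflates false positives. With positive correlation it does the opposite: the cost is power and over-wide intervals. Individual matching is itself an assumption. If the cohort is frequency-matched there are no pairs, and the remedy is adjustment for the matching factors.

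Nor is the question of vital signs and outcomes left without an analysis. The Cox model in the next sentence of the plan addresses it, so that objective does not depend on the matched comparison.

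Finally, Subject Recruitment Methods says of people who decline that "any record of their PHI will be immediately erased if electronic or shredded if on paper". It is tempting to conclude that no cohort could be built. That does not follow: nothing says decliners were the intended cohort, and patients never approached could be drawn from the hospital's Epic system, which the Design section names as the clinical data source.

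The objection leaves two facts untouched. The listed tests take no account of matching under either reading, and no objective states what the comparison is for.

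**Conclusion.** The point holds in this form. The plan names a matched comparison and gives it only independent-samples tests. For 1:1 matching with assumed within-pair correlation of 0.2 to 0.5, the nominal 5% test runs at about 2.8% to 0.6%, and power falls from 90% to about 85% to 68%. There is no loss at zero correlation. The correlation and the 1:1 ratio are assumptions, because the documents give neither.

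No objective or outcome names the comparison. If the cohort is unmonitored, which is the likelier reading but not a stated fact, the comparison is limited to health-record outcomes, and a difference is not evidence about vital signs or the monitor.

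The primary outcomes, data capture and monitor return, are not affected. This should be corrected, but it does not threaten the study's main purpose.

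**What to change.** Choose one of two changes to the Analytical Plan.

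1. **Keep the comparison.**
   - State the cohort's source, whether it is monitored, the matching variables, the ratio and the outcomes compared.
   - With individual matching, analyse by matched set: McNemar's test or conditional logistic regression for categorical variables, paired t or Wilcoxon signed-rank for continuous ones.
   - With frequency matching, adjust for the matching factors.
   - If the cohort is unmonitored, label the result a descriptive comparison of health-record outcomes that does not test vital signs or monitoring.
2. **Remove it.** Rest the objective on vital signs and outcomes on the model already planned among monitored patients. Treat length of stay as a continuous or time-to-event outcome, since it is not something a patient either has or does not have.

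The first option costs a short paragraph and slightly more analysis work. The second costs a deletion and saves building a cohort. Neither changes enrolment, visits or data collection from participants.

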**Table 2. Data Sorted into Ranges for each parameter**

Heart rate (bpm)	Systolic Blood pressure (mmHg)	Diastolic Blood Pressure (mmHg)	RR (bpm)
<50	<90	<50	<8
51-70	91-100	51-65	9-12
71-90	101-120	65-80	13-16
91-100	121-140	81-90	17-20
101-110	141-160	91-100	21-25
>110	>160	>100	>25

- Assess any correlation of range data of ambulatory preoperative VS to postoperative VS.
- Determine if specific VS ranges are associated with undesired outcomes (defined as 1) 30-day mortality, 2) hospital length of stay, c) ICU transfer rate, and 4) Rapid Response Team calls).

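### Could vital signs recorded after an ICU transfer or rapid-response call end up reported as its risk factor?

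*Combined protocol and SAP*

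**What the plan says.** Under Outcome Measure(s), two consecutive items follow Table 2. The first names both phases: "Assess any correlation of range data of ambulatory preoperative VS to postoperative VS". The second, on outcomes, names neither: "Determine if specific VS ranges are associated with undesired outcomes". The outcomes are 30-day mortality, length of stay, ICU transfer and rapid-response calls.

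The Analytical Plan summarises VS as "percent of time VS remained in one of the ranges listed in Table 2", again without a phase. For the outcomes it states: "We will use multivariable Cox proportional hazards regression modeling to assess VS risk factors associated with the postoperative undesired outcomes". It gives no time origin or censoring rule. Results are to be expressed as mean and SD, "number (percentage), odds ratio, and 95% CI", and "a P value less than 0.05 is considered significant".

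The exposure is named in the Objectives: "the percent of time the patient experiences these concerning preoperative VS values". This quantity, the sponsor expects there, "will correlate with a higher risk for a similar range of VS postoperatively, as well as undesired outcomes". The Substudy restates the hypothesis, again with preoperative VS as the predictor.

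The length of Phase II is given in Setting (24 h plus or minus 6 h from the recovery unit) and in Interventions and Interactions (during surgery and up to 24 h afterwards).

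**The concern.** Taken alone, the Analytical Plan allows percent of time from either phase to enter the Cox models. Phase II data will exist for monitored patients and overlap the period in which an ICU transfer or rapid-response call may happen. If a patient is transferred at hour 8 and monitored to hour 24, two thirds of the recording comes after the event ((24 − 8)/24 = 0.67). A fixed covariate averaged over the whole window would then carry a consequence of the event back to its cause. The rule that monitor values are not acted on does not prevent this. It stops the device from triggering an event, but the event and the care after it can still change later readings.

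At stake is the study's stated clinical hypothesis: an artefact could be published as a VS risk factor. Three lesser points touch the same models. Cox regression yields hazard ratios, yet only an odds ratio is listed. Time origin and censoring are missing. The 0.05 rule also covers outcomes that the sample size was not built for.

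**Working it through.** **The plan's own figure.** The only sample-size figure is 150, for a 12% change in VS between phases with SD 10%, two-sided 5% error and 90% power. A paired comparison gives n = (SD × (z₀.₉₇₅ + z₀.₉₀)/δ)² = (10 × (1.960 + 1.282)/12)² = 7.3, so 8 patients, or 10 by the exact t calculation (power 92.0%). The stated inputs do not yield 150, but it exceeds what they require. It bears on this point only as the number of patients.

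**Which exposure the documents name.**

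| Section | Exposure for the outcomes | Phase |
|---|---|---|
| Objectives, secondary | percent of time in concerning VS | preoperative |
| Substudy | percent of time in abnormal or concerning VS | preoperative |
| Outcome Measure(s), below Table 2 | VS ranges | not named |
| Analytical Plan | VS risk factors | not named |

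Wherever a phase is named for the outcome hypothesis, it is the preoperative one. No section names Phase II VS as a predictor of outcome. The Analytical Plan refers back to the outcome measures, which implement the Objectives. Phase I ends before surgery and the outcomes are postoperative, so no Phase I reading can follow an event.

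**What Phase II exposure would do.** The documents give no event rate, event timing, post-event VS shift or length of stay. All are assumed here, with no true VS effect.

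*Scenario A.* 150 patients; baseline abnormal share Beta(2,10); one risk covariate with hazard ratio (HR) 1.5 per SD; event rate 5% or 10%, with 20% or 40% of events in the first 24 h; monitor window 18–30 h; stay lognormal with median 96 h, log-SD 0.5 and minimum 48 h; censoring at discharge; 3000 runs per cell.

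*Scenario B.* 148 patients; event risk 5% or 10%, all within 24 h; no adjustment; about 1000 runs per cell.

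| Rise in abnormal time after event | A: rejection at 5% | A: median false HR per 10 points | B: rejection at 5% | B: median false HR per 10 points |
|---|---|---|---|---|
| 5 points | 5–8% | 1.03–1.09 | – | – |
| 10 points | 7–13% | 1.07–1.18 | 28–47% | about 1.7 |
| 20 points | 11–31% | 1.18–1.37 | 73–94% | 2.6–2.7 |
| 30 points | – | – | 91–99% | 3.6–3.8 |
| Phase I exposure instead | 4–5% | 0.98–1.00 | 3.5–5.8% | 0.97–1.04 |

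For the same 10-point rise, the two scenarios differ by a factor of about four in rejection (28/7 = 4.0; 47/13 = 3.6), largely because of when the events are assumed to occur. The sign is assumed too. If care after the event lowers abnormal time by 5 or 10 points, scenario A gives median HRs of 0.80–0.95 and rejection of 4–10%, so the artefact could hide an association instead of creating one. Both scenarios also assume that recording continues after an ICU transfer, which no section states.

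**Precision with few events.** For a covariate in SD units, var(log HR) ≈ 1/D with D events. The 95% CI factor is exp(1.96/√D), and the HR detectable with 80% power is exp(2.80/√D).

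| Assumed event rate | D = 150 × rate | CI factor | Detectable HR per SD |
|---|---|---|---|
| 5% | 7.5 | 2.05 | 2.78 |
| 10% | 15 | 1.66 | 2.06 |
| 20% | 30 | 1.43 | 1.67 |

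The intervals would be wide, but the Phase I rows above show that a single 0.05 test stays close to its nominal level at 7.5 to 15 expected events.

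**The case for a change.** The strongest case for a change is that a hypothesis is not an analysis rule. The Analytical Plan is the operative text, and it is broader than the Objectives. The item just above the outcome item separates the phases, so the omission is visible. The Substudy supports the preoperative reading imperfectly, since its example outcomes (myocardial infarction, readmission) are not those listed under Outcome Measure(s). An analyst could enter whole-window Phase II percent of time without formally departing from the plan, and a sentence naming Phase I would cost almost nothing.

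What stands is that the exposure is not restated where the models are described, and that time origin and censoring are absent. If someone did model Phase II VS against ICU transfer or rapid-response calls, readings after the event would have to be kept out.

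What does not stand is the step from silence to a flaw. Naming Phase I would repeat what the Objectives already say. A landmark rule would guard a model that is not planned, and it has costs. At an assumed 10% event rate, 15 events fall to about 9–12. A 24 h landmark also outlasts the recording of a patient monitored for 18 h, and the planned record extraction does not mention ICU or rapid-response event times.

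**Conclusion.** No change follows. The wording gap is real but minor. Read with the stated hypothesis, the exposure is preoperative, and the titled bias is then zero by design. It appears only if an analyst goes beyond that hypothesis and also averages over the whole Phase II window. Even then, the documents fix neither its size (about 5% to 99% rejection across the assumed rises) nor its direction.

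The attached points do not alter this. The odds ratio may belong to the univariate comparisons, and reporting hazard ratios from a Cox model is automatic. Time origin and censoring are choices any competent analyst makes and reports. No gain has been shown from a competing-event model for length of stay. Few events make estimates imprecise but do not invalidate the test, so dropping the 0.05 rule is a matter of reporting style.

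The conclusion rests on reading the Analytical Plan together with the Objectives and Substudy. It is helped by context: these analyses are secondary, the primary outcomes are data capture and monitor return, and monitor values do not guide care.

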### **SUBSTUDY**

Since our hypotheses are 1) the percent of time the patient experiences significantly abnormal or concerning preoperative vital signs (VS) values will correlate with a higher risk for a similar range of VS postoperatively, and 2) undesired outcomes such as myocardial infarction or higher 30-day readmission rates, we need to assure that the CareTaker monitors we use have relative accuracy. This will be important to help assure that the CareTaker device measures will be generalizable to the current standards used in clinics.

In order to investigate the accuracy and precision of heart rate (HR), systolic blood pressure (SBP), diastolic blood pressure (DBP), and oxygen saturation (SpO2) measurements of the CareTaker monitoring devices we are using, we plan to compare the values obtained by CareTaker devices to standard clinic VS measurements.

In order to accomplish this, we will measure VS using hospital-grade standard monitors at intake into the Preoperative Assessment Clinic. We will then discuss the study with the patient. If the patient accepts entry to the study, we will then place the CareTaker monitor on the patient and record the VS. We will then recheck VS with standard monitors every 20 minutes while the patient is in clinic. Within 60

seconds, each VS measure will be immediately followed by recording the VS from the CareTaker monitor.

---

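### Secondary outcome analysis: the 'concerning' preoperative vital-sign exposure is never tied to Table 2 ranges, yet every P value below 0.05 counts as significant (4, 16 or up to 96 tests, depending on the reading)

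*Combined protocol and SAP*

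**What the plan says.** **Exposure.** The secondary Objectives expect that "the percent of time the patient experiences these concerning preoperative VS values will correlate with a higher risk" of similar values after surgery and of undesired outcomes. The Substudy section restates the exposure as "the percent of time the patient experiences significantly abnormal or concerning preoperative vital signs (VS) values". Neither gives a threshold, a list of parameters or a reference to rows of Table 2.

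**Ranges.** Table 2 divides heart rate, systolic pressure, diastolic pressure and respiratory rate into six ranges each and marks none as concerning. A bullet below the table sets the task: "Determine if specific VS ranges are associated with undesired outcomes". It does not name the ranges.

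**Outcomes.** The Objectives state: "Undesired outcomes are defined as a) 30-day mortality, b) longer length of stay, c) higher ICU transfer, and 4) RRT calls". The bullet below Table 2 lists the same four. The Substudy section instead speaks of "undesired outcomes such as myocardial infarction or higher 30-day readmission rates".

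**Analysis.** The Analytical Plan describes percent of time in each Table 2 range as a descriptive statistic. For outcomes it says: "We will use multivariable Cox proportional hazards regression modeling to assess VS risk factors associated with the postoperative undesired outcomes", pointing back to the outcome measures. It lists no model terms. Its closing rule is "All P values will be two-tailed, and a P value less than 0.05 is considered significant", and the statistics to be reported include "number (percentage), odds ratio, and 95% CI". No section adjusts for the number of tests, orders them, or calls them exploratory.

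**The concern.** The plan states a directional hypothesis about death, length of stay, ICU transfer and rapid-response calls, and attaches a significance rule to it. It leaves open which exposure will be tested and how many tests will be run. Two problems follow.

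- Across the outcome analyses, the chance of reporting at least one spurious significant VS predictor exceeds 5%, by an amount that depends on a choice the plan has not made.
- Because *concerning* is undefined, even one parameter-outcome test can be tuned by picking the ranges after the outcomes are known. Neither the analyst nor the reader could then tell a planned result from a selected one.

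The sample size does not help. The 150 patients are justified by a 12% change in heart rate or blood pressure between phases, so the documents give no power or error-rate basis for the outcome associations.

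**Working it through.** The plan gives no test count or familywise error rate to reproduce, so the counts below are derived from its text.

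**Inputs from the documents.** Table 2: 4 parameters × 6 ranges = 24. Outcomes (Objectives, and the bullet below Table 2): 4. Significance level per test (Analytical Plan): 0.05, two-sided. N = 150 (Sample Size).

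**Step 1: number of tests, m.**
- One summary *concerning* exposure per patient: 1 × 4 = 4.
- One *concerning* exposure per Table 2 parameter: 4 × 4 = 16.
- Every range against every outcome: 24 × 4 = 96. Shares of time within a parameter sum to about 100%, so only about 24 − 4 = 20 ranges are free, which gives 20 × 4 = 80.

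**Step 2: error under no association.** Expected false positives = 0.05 × m, whatever the correlation. Chance of at least one, if tests are independent = 1 − 0.95^m.

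| m | Expected false positives | At least one, independent tests |
|---|---|---|
| 4 | 0.2 | 1 − 0.95^4 = 18.5% |
| 16 | 0.8 | 1 − 0.95^16 = 56.0% |
| 80 | 4.0 | 1 − 0.95^80 = 98.3% |
| 96 | 4.8 | 1 − 0.95^96 = 99.3% |

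**Step 3: allowing for correlation.** The documents give no correlations, VS distributions or event rates, so these are assumptions.
- Equicorrelated test statistics with correlation 0.3, 0.5 and 0.8: about 47%, 37% and 21% for 16 tests; 94%, 77% and 35% for 96.
- Null simulations with N = 150, a univariable Cox score test and normal VS distributions. Assumed death rates were 1-5%, and ICU-transfer and rapid-response rates 5-15%. Parameter correlations were 0-0.8 and outcome correlations 0.3 or 0.6. The results were 46-53% for 16 tests and 90-97% for 96.
- Over both approaches: about 21-53% for 16 tests and 35-97% for 96.

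**Step 4: choosing the definition afterwards.** In six ordered ranges, a contiguous block of 1 to 5 ranges can be called not concerning in 6 + 5 + 4 + 3 + 2 = 20 ways. In the simulations, one definition fixed in advance rejected in 4-5% of null data sets. Taking the best of 20 rejected in 20-27%; a repeat with a score-type test gave 19-23%.

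**Not counted.** The pre-to-postoperative correlations, the matched-cohort comparisons, and the VS without Table 2 ranges (SaO2, cardiac output, stroke volume, HRV) are left out of all three counts.

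**The case against.** The best defence is that these are secondary aims of a self-described feasibility study, whose monitor readings will not guide care. The sections can also be read together: the Analytical Plan gives the metric (percent of time in Table 2 ranges), and the Objectives give the phase (preoperative). On that view only the list of ranges is missing. Most of this stands, and it is why the point is minor. It does not remove the gap, because the feasibility label nowhere says that these P values are exploratory, and the 0.05 rule covers all of them.

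Some stronger readings are tempting but not supported:

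- **That at least 16 tests are planned.** The Objectives' wording allows one summary exposure per patient, which gives 4.
- **That myocardial infarction and readmission add further tests.** The Analytical Plan limits the Cox models to the outcomes in the outcome-measures section. The Substudy, which concerns device accuracy, mentions these two only as examples and plans no outcome analysis. The mismatch is one of wording.
- **That a false positive is nearly certain.** The 99% figure needs independence and a test of every range. The simulations assume distributions and a univariable model, whereas the plan says multivariable.
- **That the odds ratio is an error.** It can summarise the planned chi-square comparisons. Only the hazard ratio is missing.

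It is also fair to say that a Holm or Bonferroni adjustment would control the error rate. At 0.05/m, the Bonferroni thresholds are 0.0125 for 4 tests, 0.0031 for 16 and 0.00052 for 96. But m must be fixed first, and that again requires defining the exposure.

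**Conclusion.** The concern holds at minor severity and for the secondary VS-outcome analyses only. That the exposure is undefined, that multiplicity is uncontrolled, and that no exploratory label is given can all be read directly from the text and rest on no assumption.

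The size of the error does depend on the reading. Expected false positives are 0.2, 0.8 or 4.8 for 4, 16 or 96 tests. The chance of at least one is 18.5%, 56% or 99% under independence, and less under positive correlation: about 21-53% for 16 tests and 35-97% for 96. The roughly 20-27% for a definition chosen after the fact rests on assumed VS distributions.

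The primary outcomes (data capture and monitor return) are descriptive and unaffected. A reader might infer that the study's main conclusions are at risk; the documents do not support that.

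**What to change.** In the Analytical Plan:

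1. Before any outcome data are examined, the investigators list which Table 2 ranges count as *concerning* for each parameter. The exposure is the percent of Phase I (preoperative) time in those ranges.
2. Label all VS-outcome associations exploratory, including any range-by-range results. Report each estimate with its 95% CI, state how many associations were examined, and do not apply the 0.05 significance rule to them.
3. Editorial: use one outcome list in the Objectives, the Outcome Measure(s) section and the Substudy, and add the hazard ratio to the statistics to be reported.

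The cost is a few sentences and one agreed list, with no new data and no change in sample size. The study gives up significance claims for these secondary associations. A definition fixed in advance may also miss a better cut-point, although the range-by-range results can still be shown descriptively. The timing matters: a definition written after the outcomes have been seen would not remove the problem.
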